8.3.1.5. Follow-up of Adverse Events

AEs, especially those for which the relationship to study drug is “related”, should continue to be followed during the patient’s participation in the study until they have returned to baseline status or stabilized at a level acceptable to the Principal Investigator and Medical Monitor.

If after patient study completion, return to baseline status or stabilization cannot be established, an explanation should be recorded in the source documents.

8.3.1.6. Pregnancy

Pregnancies occurring in a female patient or in a male patient’s partner while enrolled in this clinical study through 1 month after the last dose of study drug administration, must be reported on a Pregnancy Reporting Form within 24 hours of the investigator, designee, or site personnel learning of the pregnancy.

Pregnancy Reporting Forms should be sent via email (preferred) or fax to:

Email: [REDACTED]

Phone: [REDACTED]

Fax: [REDACTED]

If a patient becomes pregnant while taking study drug, the study drug will be immediately discontinued and the pregnancy must be reported within 24 hours of learning of the event. The investigator will discuss the risks and concerns of investigational drug exposure to a developing fetus and counsel the subject and/or pregnant partner (or ensure such counselling is provided).

An uncomplicated pregnancy will not be considered an AE or SAE. Elective abortions without complications should not be regarded as AEs, unless they were therapeutic abortions.

Hospitalization for normal delivery of a healthy newborn should not be considered an SAE.

All pregnancies will be followed through birth. In the event there is a congenital anomaly or birth defect in a neonate or infant born to a mother exposed to study drug both the offspring and mother will be followed for 3 months post-delivery. Any congenital anomaly or birth defect in the offspring of a subject who received investigational product will be reported as an SAE. The outcome of any pregnancy and the presence or absence of any congenital anomaly or birth defect will be recorded in the source documentation and reported to the Sponsor and/or its designee.

The investigator will complete the Pregnancy Reporting Form or paper SAE form, as applicable, and report the information regarding the pregnancy, outcome, and status of the newborn, as appropriate.

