4.4. Study Duration

The estimated study duration for each patient is approximately 20 weeks and includes:

1. The screening period: up to 4 weeks
2. Treatment period: 12 weeks
3. Safety follow-up period: 4 weeks

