5.2. Inclusion Criteria

Patients who meet the following criteria will be considered eligible to participate in the clinical study:

1. Able and willing to provide signed informed consent to participate in this study
2. Males or females, age 18-75 years, inclusive, at the Screening Visit
3. Total body weight >40 kg (88 lb)
4. Diagnosis of plaque psoriasis for ≥ 6 months
5. Plaques covering $\geq 10\%$ of body surface area (BSA)
6. Psoriasis area severity index (PASI) score ≥ 12 and static Physician's Global Assessment (sPGA) score ≥ 3
7. Women of childbearing potential (WOCBP) must agree to adhere to highly effective methods of contraception for the entirety of the study and for 30 days after the last dose of study drug
8. Males who are sexually active with WOCBP must agree to use highly effective methods of contraception for the entirety of the study and for 90 days after the last dose of study drug

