5.4.2. Highly Effective Contraception

Highly effective methods of birth control are defined as those which result in a low failure rate (i.e., less than 1% per year) when used consistently and correctly.

For female patients - WOCBP:

- Combined (estrogen and progestogen containing) hormonal contraception associated with inhibition of ovulation:
 - Oral
 - Intravaginal
 - Transdermal
- Progestogen-only hormonal contraception associated with inhibition of ovulation:
 - Oral
 - Injectable
 - Implantable

Note: Hormonal contraception must be supplemented with another form of contraception that may include but is not limited to another form of highly effective contraception (e.g., IUD) or other barrier methods (such as male condom plus spermicide or female diaphragm).

- Intrauterine device (IUD)
- Intrauterine hormone-releasing system (IUS)
- Bilateral tubal ligation
- Vasectomized partner. Note that a vasectomized partner is a highly effective birth control method provided that partner is the sole sexual partner of the woman of childbearing potential trial patient and that the vasectomized partner has received medical assessment of the surgical success.
- Sexual abstinence. Sexual abstinence is considered a highly effective method only if the subject is refraining from heterosexual intercourse during the entire period of risk associated with the study treatments. The reliability of sexual abstinence needs to be evaluated in relation to the duration of the clinical trial and the preferred and usual lifestyle of the subject.
- Same sex partner

Women who have not menstruated for at least 12 months and with follicle-stimulating hormone (FSH) levels ≥ 30 mIU/mL will be considered postmenopausal and will not be required to use contraception.

For male patients with a partner of childbearing potential:

Men must agree to use two acceptable methods of contraception (e.g., condom plus spermicide), at least one of which must be a barrier method for the entire duration of the study, and for 3 months following last study drug administration.

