8.3.1.2.1. Serious Adverse Events (SAEs)

The Investigator is responsible for determining whether an AE meets the definition of an SAE. An SAE is any AE that results in any of the following outcomes:

- Death
- Life-threatening, i.e., an AE that, in the investigator's opinion, places the subject at immediate risk of death
- Inpatient hospitalization or prolongation of existing hospitalization
- A persistent or significant disability or incapacity, i.e., a substantial disruption in the subject's ability to conduct normal life functions
- A congenital anomaly or birth defect in a neonate or infant born to a mother exposed to study drug

- Significant medical events that, in the opinion of the Investigator, may jeopardize the subject or may require medical or surgical intervention to prevent any of the outcomes listed in this definition.

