8.3.1.4. Reporting of SAEs

Any AE that is serious and that occurs during the course of the study from the signing of the informed consent to end of study for each patient must be reported by the Investigator to the following:

- The Sponsor (or designee) and study monitor within 24 hours of the Investigator becoming aware of the event (expedited reporting).
- The investigation site's IRB/IEC by the Investigator in accordance with their regulations.

Initial Notification of a Serious Adverse Event (SAE)

Pharmacovigilance must be informed in writing 24 hours from the time the site investigational team first becomes aware of the event using the EDC system, as well as completing a paper SAE report forms.

A paper SAE form including a written, narrative description of any SAE must be sent via email (preferred) or fax within 24 hours after awareness of the event to:

Email: [REDACTED]

Phone: [REDACTED]

Fax: [REDACTED]

Paper SAE forms must be retained in the Investigator Site File.

In addition to reporting the SAE in the EDC and emailing the paper form, the local CRA and the Medical Monitor must be alerted via phone.

As further information regarding the SAE becomes available, follow-up information should be documented as an update using the paper SAE form. Follow-up information should be reported with 24 hours of awareness.

Related SAEs must be collected and reported regardless of the time elapsed from the last administration of study drug, even if the study has been closed.

Unrelated SAEs must be collected and reported during the study and for up to 30 days after the last dose of study medication.

SUSARs are reported to Investigators at each site and associated IRB/IEC when the following conditions occur:

- The event is an SAE
- There is reasonable possibility that the event is an adverse reaction caused by the administered drug
- The adverse reaction is unexpected, that is to say, not foreseen in the IB

Individual SUSARs considered to be a significant safety issues and/or which result in a change to the informed consent form will be reported in an expedited manner to all Investigators and IRB/IECs.

Reporting of any SAEs to applicable regulatory authorities will be the responsibility of the Local Sponsor in compliance with local regulations.

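### Routine notification of partner pregnancies stops 1 month after the last dose, although men must use contraception for 90 days; a partner pregnancy in roughly days 31 to 90 need not be notified unless an adverse outcome comes to light

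*Protocol*

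**What the plan says.** Contraception. Inclusion criterion 8 (Protocol synopsis and section 5.2) requires men who are sexually active with women of childbearing potential to use contraception "for the entirety of the study and for 90 days after the last dose of study drug". The male paragraph of section 5.4.2 gives the same duration as "for the entire duration of the study, and for 3 months following last study drug administration". For women, inclusion criterion 7 sets the period as "for the entirety of the study and for 30 days after the last dose of study drug".

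Notification. Section 8.3.1.6 applies a single window to women in the trial and to the partners of men in it. For men, the rule is that a pregnancy in the "partner while enrolled in this clinical study through 1 month after the last dose of study drug administration, must be reported". The report goes on a dedicated form and is due 24 hours after the site becomes aware. The section also says that an uncomplicated pregnancy is neither an AE nor an SAE, and that all pregnancies are followed through birth.

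Outcomes. The SAE definition in section 8.3.1.2.1 lists "A congenital anomaly or birth defect in a neonate or infant born to a mother exposed to study drug". The 3-month follow-up of infant and mother in section 8.3.1.6 is likewise limited to an exposed mother. A later sentence of 8.3.1.6 is wider: a congenital anomaly in the child of any treated subject is reported as an SAE, with no stated cut-off. Section 8.3.1.4 adds: "Related SAEs must be collected and reported regardless of the time elapsed from the last administration of study drug". Unrelated SAEs are collected only up to 30 days after the last dose.

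Contact. Section 4.4 lists "Safety follow-up period: 4 weeks". The Schedule of Assessments puts Week 12 at Day 84 and the last visit at Day 115.

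**The concern.** The sponsor asks treated men to avoid conception for 90 days after dosing, but asks sites to notify partner pregnancies for only about the first third of that time. The single window fits the female rule and appears to have been applied to men without adjustment; the documents give no reason for it.

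Notification of partner pregnancies is how paternal exposure to an unapproved drug would be recorded, counselled and followed to birth. Outside the window, a pregnancy would reach the sponsor only if something went wrong and someone volunteered it. Normal outcomes would not be recorded, so an adverse one could not be set against the number of pregnancies exposed. With so few such pregnancies expected, each carries information.

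**Working it through.** The plan states no figure of its own on this point, so the check is day arithmetic and then a bound on expected events.

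**1. Length of the gap**
- Male contraception after the last dose: 90 days (inclusion criterion 8); section 5.4.2 says 3 months, or 90 to 92 days.
- Notification after the last dose: 1 month (section 8.3.1.6), or 28 to 31 days.
- Gap against 90 days: 90 − 31 = 59 and 90 − 28 = 62 days; with a 30-day month, 90 − 30 = 60.
- Share uncovered: 59/90 = 65.6%; 62/90 = 68.9%.
- Reading 3 months as up to 92 days, the largest gap is 92 − 28 = 64 days (69.6%).

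**2. The same comparison for women**
- 30 days (inclusion criterion 7) less 28 to 31 days gives +2 to −1 days. There is in effect no gap.

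**3. Scheduled contact**
- Last dose on Day 84 and last visit on Day 115: 115 − 84 = 31 days.
- End of the male contraception period: 84 + 90 = Day 174.
- Days with no scheduled contact: 174 − 115 = 59.

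**4. Do other provisions cover these days?**
- Related SAEs have no time limit, but an uncomplicated pregnancy is not an SAE.
- The sentence on anomalies in any treated subject's child has no cut-off. It applies only once an anomaly is known, and does not provide for notifying or following the pregnancy.
- Follow-up through birth can operate only on pregnancies that the site learns of, and the notification window governs which of those must be sent in.
- A patient who stops the drug early but stays in the study may still be enrolled more than 1 month after the last dose. The text still ends the window at 1 month, so for such patients it is at best ambiguous.

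**5. Expected events**
- Rate (assumption): 1% per couple-year, the ceiling that section 5.4.2 gives for highly effective methods.
- Per couple over the gap: 1 − 0.99^(59/365) = 0.00162; 1 − 0.99^(62/365) = 0.00171.
- Active-arm patients: 5 × 35 = 175. The documents give no sex split, so the number of men with a partner of childbearing potential who do not enter the extension study is assumed to be 25 to 125.
- Expected pregnancies: 25 × 0.00162 = 0.04; 125 × 0.00171 = 0.21.
- To reach one expected pregnancy with 125 couples, the yearly rate r must satisfy 125 × [1 − (1 − r)^(62/365)] = 1. Then r = 1 − 0.992^(365/62) = 4.6%, more than four times the assumed rate.

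**The case against.** The strongest objection is that the two windows serve different purposes. Contraception is a precaution asked of the patient, and notification is a duty placed on the site. No instruction contradicts another, nothing in the documents says that they must match, and the reason for the 90 days is not in the text supplied. This stands in part: calling the 90 days a period of known risk would be an inference. The point needs only that the sponsor chose 90 days as its own precaution period and does not routinely collect the partner pregnancies that occur in most of it.

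A reader might infer that nothing at all is reportable after 1 month. The documents do not support that. Section 8.3.1.6 makes an anomaly in any treated subject's child an SAE without a cut-off, and section 8.3.1.4 makes related SAEs reportable at any time. The gravest outcome therefore has a reporting duty once known; what is missing is notification and follow-up of the pregnancy itself.

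A reader might also infer that the maternal wording in section 8.3.1.2.1 excludes paternal exposure from SAE reporting. It does not, because the wider sentence in 8.3.1.6 can be followed alongside it. Only the 3-month infant follow-up is truly confined to exposed mothers.

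The consent form and the extension-study protocol are not among the documents and might add coverage. Entry to the extension is conditional (section 6.9), so coverage there cannot be assumed either way. Finally, the expected count is tiny and its inputs are assumed. That is accepted; it limits the weight of the point but does not remove the mismatch.

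**Conclusion.** The point holds for routine notification. As written, a partner pregnancy in roughly days 31 to 90 after the last dose need not be notified or followed unless an adverse outcome comes to light. About 60 of the 90 days are affected (59 to 62), while the female windows agree to within 2 days.

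The weakness is in ascertainment and does not imply many events. The estimate of 0.04 to 0.21 pregnancies rests on the assumed 1% yearly rate and the assumed 25 to 125 couples. The upper end is extreme: it takes 125 of 175 active-arm patients (71%) to be men with a partner of childbearing potential who do not enter the extension. The 1% rate is also only an anchor, since the documents give no failure rate for the two-method rule for men in section 5.4.2. Efficacy, power and the timing of the analyses are unaffected. The correction is worth making because it is specific and cheap.

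**What to change.** In section 8.3.1.6, split the window. Keep 1 month after the last dose for pregnancies in female patients, and make pregnancies in partners of male patients reportable through 90 days after the last dose. At the last visit, tell men to report a partner's pregnancy up to that date.

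Extend the 3-month infant follow-up in 8.3.1.6, and the congenital-anomaly item in 8.3.1.2.1, to the offspring of any exposed subject. The later sentence of 8.3.1.6 already does this for SAE reporting.

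The cost is a wording amendment, with the ethics and, where needed, competent-authority approvals that section 11.2 requires, plus a line in the consent form. Safety reporting for these men would run passively for about 59 days past the last visit, and following a pregnancy would need the partner's agreement.

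No added call or visit is needed. A scheduled contact near Day 174 would be a protocol activity after the last visit and could delay completion as section 4.5 defines it. Reports can go through the safety database, so the Week 12 and Week 16 analyses need not wait.

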8.3.2. Clinical Laboratory Assessments

Samples for clinical laboratory assessments will be collected at the time points detailed in the Schedule of Assessments (see [Section 1.3](#)).

Laboratory safety tests may be performed at unscheduled time points, if deemed necessary by the Investigator. Screening laboratory safety tests may be repeated upon discussion with the Sponsor/Medical Monitor.

The Laboratory Manual will supply complete written instructions for collection, handling, processing, storage, and shipping of samples.

8.3.3. Vital Signs

Vital signs will be assessed at the time points detailed in the Schedule of Assessments (see [Section 1.3](#)). The following vital signs will be measured:

- Blood pressure (systolic and diastolic [mmHg])
- Heart rate (bpm)
- Body temperature (°C)

BP and heart rate recordings will be made after the patient has been resting supine or semi-recumbent for ≥ 5 minutes.

8.3.4. Electrocardiograms

12-lead ECGs will be performed at time points detailed in the Schedule of Assessments (see [Section 1.3](#)).

The 12-lead ECGs will be performed after the patient has been resting supine or semi-reclined for ≥ 5 minutes. The ECG paper tracing will be assessed by the study investigator for any abnormality and for clinical significance. The ECG parameters that will be measured include but are not limited to: PR interval, QRS interval, RR interval, QT interval, and QTc.

The ECGs will be sent electronically to a central location to be analyzed and over-read. The study site should review the centrally read report as soon as possible once available. The central report findings should be compared to the local paper ECG findings reported by the site. Any difference in reported ECG findings should be reconciled by the Investigator. The study team does not require a report back from this central location to act on any findings identified on the paper ECG tracing that, in the opinion of the study investigator, are clinically significant.

8.3.5. Physical Examinations

Physical examinations will be performed at the time points detailed in the Schedule of Assessments (see [Section 1.3](#)).

Complete Physical Examination

An assessment of general appearance and a review of systems (dermatologic, head, eyes, ears, nose, mouth/throat/neck, thyroid, lymph nodes, respiratory, cardiovascular, gastrointestinal, extremities, musculoskeletal, neurologic and psychiatric systems). A gynecological or genital examination is not required unless it is deemed necessary in the opinion of the Principal Investigator.

Abbreviated Physical Examination

An assessment of the general appearance, skin, cardiovascular system, respiratory system and abdomen and any symptom-driven assessment as appropriate.

The abbreviated physical examination should be extended to a full physical examination based on the clinical condition of the patient and if considered necessary by the Principal Investigator.

8.4. Pharmacokinetic Assessments

Blood samples for the analysis of plasma concentration levels of ESK-001 (PK) and ESK-001 metabolites will be collected at the time points detailed in the Schedule of Assessments (see [Section 1.3](#)).

Samples will be used to evaluate the PK of ESK-001 and its metabolites. Samples collected for analyses of ESK-001 and ESK-001 metabolite plasma concentrations may also be used to evaluate safety or efficacy aspects related to concerns arising during or after the study. After the blood samples are analyzed for plasma ESK-001 and ESK-001 metabolite concentrations, any residual samples may be used for exploratory analysis such as additional metabolite profiling and identification, interacting drug concentration measurements, ex vivo protein binding, or development of PK or PD assays.

Details regarding the collection, handling, processing, storage and shipping of samples will be provided in the Laboratory Manual.

8.5. Pharmacodynamic Assessments

Samples for the exploratory analysis of ESK-001 PD effects will be collected at the time points detailed in the Schedule of Assessments (see [Section 1.3](#)).

Details regarding the collection, handling, processing, storage and shipping of samples will be provided in the Laboratory Manual.

8.5.1. Skin Biopsy and Tape Stripping (Skin Biomarker Profile)

Skin samples will be collected via skin biopsy and/or tape-stripping at time points specified in the Schedule of Assessments for patients who provide specific consent. The samples will be used to assess skin biomarker response for a number of exploratory purposes that may include but are not limited to studying the ESK-001 mechanism, patient treatment response, and disease progression.

8.5.2. Plasma Biomarker Profile

Plasma-based samples will be collected at time points specified in the Schedule of Assessments to assess blood-based biomarker response for a number of exploratory purposes that may include but are not limited to studying biomarkers of ESK-001 mechanism, treatment response, and disease progression.

8.5.3. Blood RNA-seq Profile (Exploratory Transcriptomics)

RNA-based samples will be collected at time points specified in the Schedule of Assessments to assess transcriptomic biomarker response for a number of exploratory purposes that may include but are not limited to studying the mechanism of ESK-001, patient treatment response, and disease progression.

8.5.4. Blood Cell-Based Biomarkers

Whole blood will be collected at timepoints specified in the Schedule of Assessments to assess the response of immune-stimulated biomarkers for a number of exploratory purposes that may include but are not limited to studying biomarkers of ESK-001 mechanism, treatment response, and disease progression.

8.6. Genetics

Unless prohibited by local ethics committees, a DNA sample will be collected from patients who provide specific consent. The sample will be used for genetic analyses that may include but are not limited to patient-specific ESK-001 metabolism, drug-transport, and ESK-001 response.

9. SAFETY MONITORING COMMITTEE

A Safety Monitoring Committee (SMC) will be convened to review the safety data throughout this study. The SMC will consist of the Sponsor's Medical Director; the study Medical Monitor (from the CRO); two independent physicians with clinical trial experience, one with dermatology expertise and the other a cardiologist; and an independent statistician.

The SMC may meet at any time during the study to review blinded (or unblinded, if required) data when deemed necessary by the SMC.

The SMC will initially convene to review all available safety data after approximately 50 patients have been randomized and completed their Week 4 visit. The SMC will also meet regularly thereafter, based upon accumulating safety data and patient enrollment. The final prescheduled meeting of the SMC will be after study completion; to evaluate all safety data from all patients enrolled in the study. The SMC may also review safety data from eligible patients who complete this study and who enter an ESK-001 open label extension study.

The roles and responsibilities of SMC members and the SMC procedures and communication pathways are detailed in the SMC Charter.

